7.4.4 Phase 2 Study Treatment: Dexamethasone

Dexamethasone is a synthetic glucocorticoid with low mineralocorticoid activity.

Dexamethasone is supplied as tablets intended for oral administration.

Dexamethasone may increase the risk of infection or psychiatric disorders; information on special precautions and warnings may be found in the package insert. Additional information on the product presentation, formulation, storage, and administration of dexamethasone may also be found in the package insert.

7.4.4.1 Dexamethasone Administration

For subjects assigned to BION-1301+DEX, instruct the subject to take 40 mg PO QW at home in the morning on Days 1, 8, 15, and 22 of each cycle (prior to clinic visit, if scheduled). The dose

should preferably be taken in the morning to minimize insomnia, and prior to any scheduled BION-1301 dosing.

Subjects > 75 years of age or BMI < 18.5 may receive dexamethasone at 20 mg per Investigator discretion. Other dose modifications are allowed based on Investigator discretion and written approval from Medical Monitor (Section 7.4.5.2).

At the end of dexamethasone treatment, the dose may be tapered if required in a stepwise fashion per Institutional practice.

7.4.5 Dose Modifications and Dosing Interruptions

Dose modifications and/or interruptions are recommended for subjects who do not tolerate the protocol-specified dosing schedule.

Following the first 4 cycles of study treatment, dosing interruptions are also permitted in the case of medical / surgical events, palliative radiation, or logistical reasons not related to study therapy (e.g. elective surgery, unrelated medical events, vacation, and/or holidays). Subjects should be placed back on study therapy within 3 weeks of the scheduled interruption, unless otherwise discussed with the Sponsor. The reason for interruption should be documented in the subject's study record.

7.4.5.1 Dose Modifications for Suspected BION-1301-related Events

The following general dose modification guidelines will be applied for suspected BION-1301-related events:

- If a subject experiences a DLT at any point during the study, study drug should be withheld. Consult the Medical Monitor prior to resuming treatment following the occurrence of a DLT.
- Generally if a dose is interrupted or withheld for AE, treatment may be resumed at the same (or lower) dose level on the same dosing schedule following resolution of the AE to Grade 1 or baseline.
 - If the Investigator considers it in the subject's best interest to resume treatment before the AE has resolved to Grade 1, the Medical Monitor should first be consulted.
 - Reductions in study drug dose must be approved by the Medical Monitor.
 - If the subject is on a QW dosing schedule; frequency may be reduced to Q2W following consultation with the Medical Monitor.
- If dose interruptions persist > 6 weeks (from the expected day of dosing), the subject will be discontinued from the study unless there is evidence of clinical benefit and the Investigator deems it is in the subject's best interest to remain on study. In such cases, the Medical Monitor must be consulted.
- If a subject requires more than 2 dose reductions/modifications for the same toxicity, BION-1301 should be discontinued.

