7.2 End of Study

The end of the study is defined as the date when all subjects have completed the final protocol-specified safety assessment and/or discontinued study participation (withdrawal of consent or lost to follow-up), whichever occurs first (estimated to be approximately 18 months from the last subject commencing treatment). Following the in-clinic portion of study additional biomarker analyses may take place prior to Clinical Study Report submission. At end of the study, all remaining subjects will be offered enrollment in a long-term follow-up study for survival.

The Sponsor may terminate the study at any time for any reason. Should the study be terminated, subjects will be contacted to complete the End of Treatment (EOT) visit and protocol-defined safety follow-up procedures.

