7.3.3 Subject Discontinuation

Subjects will be encouraged to complete the study; however, a subject may voluntarily withdraw from treatment or the study at any time. The Investigator will provide a reason for discontinuation from treatment. Subjects who wish to discontinue treatment will be encouraged to complete EOT and Follow-up assessments.

A subject in this clinical study may be discontinued from treatment for any of the following reasons:

- The subject withdraws consent or requests discontinuation for any reason
- Occurrence of any medical condition or circumstance that exposes the subject to substantial risk and/or does not allow the subject to adhere to the requirements of the protocol
- Confirmed disease progression
- Any DLT, serious adverse event (SAE), clinically significant adverse events (AEs), severe laboratory abnormality, intercurrent illness, or other medical condition which indicates to the Investigator that continued participation is not in the best interest of the subject
- Pregnancy
- Subject failure to comply with protocol requirements or study-related procedures
- Termination of the study by the Sponsor or regulatory authority

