7.5 Study Assessments and Procedures

Screening assessments will be conducted to confirm eligibility and to obtain baseline measurements. Screening must be completed within 28 days prior to first dose of study drug. An enrollment form will confirm subject eligibility after completion of all screening procedures. Subjects must initiate dosing of study drug within 2 weeks from the date of the approved enrollment form.

Subjects will be requested to complete multiple clinic visits during the initial two dosing cycles; visit frequency is reduced beginning at Cycle 3 and beyond. An EOT Visit will occur 28 days after the last dose of study drug. If the subject begins another anticancer therapy before the end of the 28-day period, all EOT Visit assessments should be completed prior to commencing the new therapy. Unresolved AEs will be monitored until resolution or confirmed stability of the event.

Subjects who discontinue study treatment for reasons other than progressive disease should continue tumor response assessments as per the standard of care frequency until disease progression is documented, withdrawal of consent, or study end.

Follow-up calls will occur every 12 weeks after the last dose of study drug. Data will be collected on survival and any subsequent cancer-related therapies. Telephone contact(s) should also be scheduled to satisfy safety reporting requirements as specified in [Table 7-4](#).

All study visits (and visit windows), assessments, and procedures will be performed as indicated in the Schedule of Events ([Table 2-1](#)). On days when study drug is administered, assessments should be performed prior to dosing unless otherwise specified. Further details of study procedures and assessments can be found in the Study Reference and Laboratory Manuals.

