8.4 Pregnancy Reporting

If the subject or partner of a subject participating in the study becomes pregnant during the study or within 28 days of discontinuing study drug (or if the subject initiates new anticancer therapy, whichever is earlier) the Investigator should report the pregnancy and any follow-up information to the Sponsor or its designee within 24 hours of awareness of the information.

A subject becoming pregnant while on study drug will immediately be withdrawn from the study and Early Termination study procedures will be performed as appropriate. The investigator should counsel the subject, discussing any risks of continuing the pregnancy and any possible effects on the fetus.

Abortion, whether therapeutic, accidental, or spontaneous, should be reported as an SAE. Similarly, any congenital anomaly or birth defect in a child born to a subject exposed to the study drug should be reported as an SAE.

Monitoring of the subject or partner and pregnancy should occur until the conclusion of the pregnancy or final outcome. Report the outcome, including any premature termination. Follow live births for a minimum of 30 days or until the first well-baby visit. Any relevant information received by the Investigator after these time periods will be forwarded to the sponsor.

If the subject gives permission for her primary physician to be informed, the Investigator is to notify the subject's primary physician that she was participating in a clinical study at the time she became pregnant, and provide details of the treatment that the subject received.

The pregnancy reporting form along with the form completion instructions are provided in the Investigator study files.

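### Protocol Section 7.4.5.1 takes subjects with interruptions over 6 weeks off the study, which conflicts with the sections that continue follow-up after treatment stops

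*Protocol*

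**What the plan says.** The rule is in the Protocol's dose-modification list, Section 7.4.5.1: "If dose interruptions persist > 6 weeks (from the expected day of dosing), the subject will be discontinued from the study unless". The exception begins "unless there is evidence of clinical benefit and the Investigator deems it is in the" subject's interest to stay, and it requires consultation with the Medical Monitor. The next bullet of the same list handles another toxicity exit differently: "If a subject requires more than 2 dose reductions/modifications for the same toxicity, BION-1301 should be discontinued". That bullet stops the drug and says nothing about leaving the study.

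Other sections keep the two exits apart:

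- Section 7.3.3 introduces its list, which includes DLTs, SAEs, other adverse events and pregnancy, with "A subject in this clinical study may be discontinued from treatment for any of the following reasons". Subjects who wish to stop treatment are encouraged to complete the EOT and follow-up assessments.
- Section 7.5 states: "Subjects who discontinue study treatment for reasons other than progressive disease should continue tumor response assessments as per the standard of care frequency", until progression, withdrawal of consent or study end. Section 7.5.2.2 repeats this.
- Table 7-4 and the text below it run SAE reporting, with a telephone contact, to 90 days after the last dose.
- The synopsis continues survival follow-up after study drug stops.
- Section 7.2, in defining the end of the study, refers to subjects who have "discontinued study participation (withdrawal of consent or lost to follow-up". It names no other way of ending participation.

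Section 8.4 has a parallel conflict: "A subject becoming pregnant while on study drug will immediately be withdrawn from the study". Section 7.3.3 lists pregnancy as a reason to stop treatment.

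**The concern.** A site with a subject on a long hold has two instructions. Section 7.4.5.1 ends the subject's time on the study. The other sections end treatment and keep collecting data. Nothing in 7.4.5.1 says that response assessments or the 90-day SAE contact continue after the exit.

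The subjects concerned are a selected group. The rule applies to holds for suspected drug-related events, and its exception retains those with evidence of benefit. Those who leave are therefore the subjects who have not tolerated the drug and have no such evidence. Missing data in this group would depend on both tolerability and outcome. A subject who stops under the next bullet, also for toxicity, stays in follow-up.

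The distinction also matters for reporting. The SAP tabulates study status and treatment status separately, each with reasons (Section 6.2). It computes duration on study from the end-of-study date (Section 5.3) and includes data up to completion of or withdrawal from the study (Section 4, Precision).

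**Working it through.** The plan states no figure for this rule, so there is none to reproduce. The check is a day count from the last dose.

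**Inputs**
- Length of hold: 6 weeks = 42 days, counted from the expected dosing day (Section 7.4.5.1).
- Dosing interval: 7 days nominal for QW, with 5 to 8 allowed; 14 days for Q2W (Tables 2-1 and 2-2).
- AE window: 28 days after the last dose (Table 7-4).
- EOT visit: day 28, with +7 days allowed (Table 2-1).
- SAE window: 90 days after the last dose (Table 7-4).

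**Formulas**
- Trigger day = dosing interval + 42.
- SAE days remaining = 90 − trigger day.

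| Schedule | Trigger day | Days past day 28 | SAE days left | Share of 90 |
|---|---|---|---|---|
| QW | 7 + 42 = 49 | 21 | 90 − 49 = 41 | 46% |
| Q2W | 14 + 42 = 56 | 28 | 90 − 56 = 34 | 38% |

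**Sensitivity to visit timing**
- QW intervals of 5 to 8 days put the trigger at day 47 to 50, leaving 43 to 40 days.
- Q2W with a ±3-day window (11 to 17 days) puts it at day 53 to 59, leaving 37 to 31 days.

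**What lies outside the loss**
- The 28-day AE window and the nominal EOT visit both come before the trigger. Even an EOT visit at day 35 precedes it by 14 days (QW) or 21 days (Q2W).
- Unresolved AEs and SAEs are followed to resolution or stability (Sections 7.5, 8.1 and 8.3.4), so the event that caused the hold remains under follow-up.
- New SAEs assessed as possibly or probably related are reportable even outside the window (Table 7-4).
- If new anti-cancer therapy starts, the SAE window is 28 days. None of the 41 or 34 days is then at stake.
- Section 7.5.2.3 asks sites to try to obtain survival status for subjects who withdraw from the study, so survival is partly protected.

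What remains exposed is active ascertainment of new SAEs from the trigger to day 90, and all response assessment after the trigger.

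**The case against.** The strongest reply is that this is loose drafting and the intended meaning is plain. Section 7.4.5.1 concerns dosing, so its exception for staying on study reads naturally as staying on treatment. Section 7.5.2.2.1 uses study discontinuation to describe a treatment decision. The 90-day contact and the continued response assessments are tied to the last dose or to stopping treatment, with no exemption for long holds. If Section 7.2 recognises only consent withdrawal and loss to follow-up, then 7.4.5.1 cannot end participation at all.

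Much of this stands. Removal from follow-up is only the literal reading, and a site could reasonably follow the other sections. But the next bullet shows that the same list can name the drug when it means the drug, and the SAP gives leaving the study its own consequences. Where two readings are open, sites may differ.

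A reader might infer more, in three ways the documents do not support:

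- **That every subject with a long toxicity hold is dropped.** The clinical-benefit exception prevents this.
- **That PFS was biased, or that a difference between arms would be distorted.** PFS is a Phase 2 endpoint. Phase 2 was not enrolled (SAP Section 3.6), its analyses are omitted (SAP Section 10), and no inferential comparison of arms was planned (Protocol Section 7.6.2). For DOR the exposure is narrower still, because a responder would ordinarily have the evidence of benefit that opens the exception.
- **That a known share of subjects is affected, or that sites close out the subject's record at this point.** The documents report no count of holds over 6 weeks and describe no such step.

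**Conclusion.** The conflict is real and goes beyond wording, because it decides whether late safety and response data are sought in subjects with long holds and no evidence of benefit. Per affected subject, the loss is at most 41 of 90 SAE days (QW) or 34 of 90 (Q2W) at nominal intervals, plus later response assessments. This assumes that the site applies 7.4.5.1 literally and that no new anti-cancer therapy starts. The number of affected subjects cannot be derived from the documents.

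For the Phase 1 report, the effect is on SAE capture, the listed responses, disposition and time on study. Censoring of PFS and DOR for a reason linked to toxicity and lack of benefit (Protocol Sections 7.6.5.1 and 7.6.5.2) is a weakness of the Phase 2 design only. For pregnancy the effect is narrower, since Section 8.4 itself requires follow-up of the pregnancy to its outcome.

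**What to change.** Reconcile Sections 7.4.5.1 and 8.4 with Sections 7.2, 7.3.3, 7.5, 7.5.2.2 and Table 7-4, so that leaving treatment and leaving the study are distinct throughout. State that the EOT visit, the 90-day SAE contact, response assessments and survival follow-up continue unless the subject withdraws consent or is lost to follow-up. This concerns only what is collected afterwards. No view is taken on the length of an interruption or on when drug should stop.

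The sponsor terminated the study on 07 May 2019 after enrolling 21 subjects (SAP Section 3.1), so a protocol edit alone would do little for this trial. The study report should therefore also say whether any of the 21 left under the 7.4.5.1 rule and, for each, how far SAE and response follow-up ran after the last dose.

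The cost is two wording changes and a check of disposition records. The follow-up itself is already specified for other subjects who stop treatment for reasons other than progression.

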7.4.5.2 Dose Modifications for Suspected Dexamethasone-related Events

Dose modifications are allowed for suspected dexamethasone-related events or intolerance based on Investigator discretion.

Subjects who experience unacceptable toxicity directly attributable to dexamethasone may continue on study and receive BION-1301 as a single agent following Medical Monitor approval.

If dexamethasone is discontinued, the dose may be tapered (if required) in a stepwise fashion until a complete stop per Institutional practice.

7.4.6 Concomitant Medications and Procedures

Subjects may receive concomitant medications and procedures as required or deemed necessary for supportive care, unless specifically restricted or prohibited in this study (Section 7.4.7).

During the course of the study, subjects are anticipated to continue the use of prescribed medications identified during the screening procedures, consistent with study inclusion and exclusion criteria.

Antihypertensive therapy is allowed as concomitant medication; however, because transient hypotension has occurred during infusions of monoclonal antibodies, consideration should be given to withholding antihypertensive medications for 12 hours prior to infusion of BION-1301.

7.4.7 Prohibited Medications and Procedures

A subject may be discontinued from study treatment for use of prohibited medications or procedures. Approval must be obtained from the Medical Monitor for a subject to continue dosing if a prohibited medication is administered within the specified timeframes. The following therapies are not permitted or are restricted during the study:

- Non-study chemotherapy, small molecule, anticancer-directed hormonal therapy, immunotherapy, or other therapeutic monoclonal antibodies (approved or investigational)
- ASCT or bone marrow transplant
- Radiation therapy (dosing interruption allowed for palliative radiation)
- Plasmapheresis
- Any other investigational product or device
- Systemic corticosteroids > 10 mg/day of prednisone or equivalent (except use of dexamethasone as study treatment, or corticosteroids used to treat infusion-related reaction [[Section 7.4.3.1.3](#)])
- Biotin supplements at doses higher than recommended Daily Value (300 mcg)
- Live viral vaccines (BION-1301+DEX arm in Phase 2 only)

There are no prohibited therapies or procedures once the subject has completed the EOT visit.

7.4.8 Treatment Compliance

BION-1301 will be administered by a qualified health care professional at an approved study site. The date, time, and volume of each dose of BION-1301 administered to each subject must be recorded in the source document. If assigned to BION-1301+DEX, treatment compliance (i.e. date and time of dose) for dexamethasone will be self-reported by the subject in a diary. The objective is 100% compliance, and Investigators and site personnel should evaluate compliance at each visit and take appropriate steps to optimize compliance.

7.5 Study Assessments and Procedures

Screening assessments will be conducted to confirm eligibility and to obtain baseline measurements. Screening must be completed within 28 days prior to first dose of study drug. An enrollment form will confirm subject eligibility after completion of all screening procedures. Subjects must initiate dosing of study drug within 2 weeks from the date of the approved enrollment form.

Subjects will be requested to complete multiple clinic visits during the initial two dosing cycles; visit frequency is reduced beginning at Cycle 3 and beyond. An EOT Visit will occur 28 days after the last dose of study drug. If the subject begins another anticancer therapy before the end of the 28-day period, all EOT Visit assessments should be completed prior to commencing the new therapy. Unresolved AEs will be monitored until resolution or confirmed stability of the event.

Subjects who discontinue study treatment for reasons other than progressive disease should continue tumor response assessments as per the standard of care frequency until disease progression is documented, withdrawal of consent, or study end.

Follow-up calls will occur every 12 weeks after the last dose of study drug. Data will be collected on survival and any subsequent cancer-related therapies. Telephone contact(s) should also be scheduled to satisfy safety reporting requirements as specified in [Table 7-4](#).

All study visits (and visit windows), assessments, and procedures will be performed as indicated in the Schedule of Events ([Table 2-1](#)). On days when study drug is administered, assessments should be performed prior to dosing unless otherwise specified. Further details of study procedures and assessments can be found in the Study Reference and Laboratory Manuals.

7.5.1 General (Baseline) Assessments

7.5.1.1 Informed Consent

Before any screening or study-specific procedure is performed, an individual must be given a complete explanation of the purpose and requirements of the study, and an informed consent form (ICF) approved by the Institutional Review Board and/or Ethics Committee (IRB/EC) and an authorization for use and disclosure of protected health information must be signed. An

original signed consent form will be retained in the subject's source documentation at the site; a copy will be provided to the subject.

Assessments conducted as standard of care prior to informed consent may be considered for eligibility requirements if performed within the required Screening Period.

7.5.1.2 Eligibility

Potential subjects will be evaluated for entry into the study according to the stated inclusion and exclusion criteria ([Section 7.3](#)). Individuals deemed ineligible for study enrollment do not need to complete all screening procedures. The reason for ineligible status will be documented. Tests with results that fail eligibility requirements may be repeated once during the Screening Period if the Investigator believes the results to be in error. Additionally, a subject who fails Screening may repeat the process one time if the Investigator believes there has been a change in eligibility status (e.g. after recovery from an infection).

For subjects who meet all inclusion/exclusion criteria, an enrollment form will be completed and sent to Sponsor or designee for review and approval. The first dose of study drug will not be administered until the Investigator receives approval of the enrollment form.

7.5.1.3 Demographics, Medical History, and Height

Demographic data and a complete medical history will be collected at Screening by the Investigator or qualified designee. Demographic information (as allowed by local regulations) will include date of birth, age, gender, ethnicity, and race. Medical history should include all active conditions and any condition considered to be clinically significant by the Investigator.

Details regarding the disease for which the subject has enrolled in this study (e.g. date of diagnosis, primary tumor histology, prior surgery(ies), radiation therapy, chemo- and biological therapies, and stage of cancer) will be recorded.

Height will be obtained at Screening with a stadiometer. Body mass index will be derived using height and weight.

